### **13.6 Analysis of Exploratory Endpoints**

The pharmacodynamic, ctDNA, CTC and tissue biomarker studies (including but not limited to DNA sequencing, RNA-Seq and immunohistochemistry) are considered exploratory. Within the group of patients who begin treatment with palbociclib and ganitumab, the mean, standard deviation, and median relative change from baseline will be calculated for each marker. ctDNA positivity will be tested for association with PFS and OS using a log-rank test, and quantified with hazard ratios. Association between continuous measures of modulation of these markers versus a) occurrence of any DLT and b) clinical response of partial response or better will be tested using a Wilcoxon rank-sum test and presented descriptively using box and whisker plots. Secondary somatic mutations will be analyzed from tumor material and tested for association with objective response using Fisher's Exact test.

Graphical presentation of tumor marker data will be key to hypothesis development. Spaghetti plots will be used to display the serial measurements of ctDNA and IGF-1 related serum proteins.

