#### 1.4 Correlative Biology Objectives

1.4.1 To evaluate serial measurements of circulating tumor DNA burden as a surrogate marker of response to protocol therapy.

1.4.2 To evaluate serial measurements of IGF-1 related serum proteins as potential pharmacodynamic markers of IGF pathway inhibition.

1.4.3 To explore secondary somatic mutations and tumor protein and RNA markers as potential predictive markers of clinical benefit from the combination of palbociclib and ganitumab.

1.4.4 To bank tumor material, germline DNA, and peripheral blood for potential future research for participating subjects who provide additional consent.

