### 13.2 Sample Size, Accrual Rate and Study Duration

A total of 15 response evaluable patients with Ewing sarcoma (Cohort A) and 12 response evaluable patients with SDH-deficient GIST (Cohort B) will be required to address the primary objective. Patients who are not eligible and/or evaluable for response will be replaced.

Therefore, given potentially inevaluable patients a maximum of 33 patients with Ewing sarcoma or SDH-deficient GIST are expected to enroll.

Study Duration: We anticipate that 1-2 patients with Ewing sarcoma and 1-2 patient per GIST per month will be available for enrollment. Enrollment of the maximum sample size of 33 patients with Ewing sarcoma and GIST will require approximately 18-24 months.

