### **13.5 Analysis of Secondary Efficacy Endpoints**

Progression-free survival (PFS) will be defined as the time from study enrollment to first episode of disease progression or death due to disease, with patients without event censored at last follow-up. Overall survival (OS) will be defined as the time from study enrollment to death, with surviving patients censored at last follow-up. PFS and OS will be estimated using Kaplan-Meier methods separately for each cohort, with standard errors according to Greenwood.

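### Section 13.6 does not split or stratify the exploratory marker tests by cohort, so read plainly they pool Ewing sarcoma with SDH-deficient GIST and can mistake disease for a marker effect.

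*Combined protocol and SAP*

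**What the plan says.** Section 13.6 opens the marker analyses with a single group, "Within the group of patients who begin treatment with palbociclib and ganitumab", for which means, standard deviations and median relative changes are computed. The tests follow:

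- ctDNA: "ctDNA positivity will be tested for association with PFS and OS using a log-rank test, and quantified with hazard ratios".
- Continuous marker changes against any DLT and against response of PR or better: "will be tested using a Wilcoxon rank-sum test and presented descriptively using box and whisker plots".
- Secondary somatic mutations: "tested for association with objective response using Fisher's Exact test".

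None of these sentences names a cohort, a stratification factor or an adjustment, and sections 1.4, 2.5 and 9.1 do not supply one.

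The rest of section 13 does. Response is tested by cohort (13.3.2), toxicity is tabulated by cohort (13.3.3), and the DLT rules are separate (13.4). For the time-to-event endpoints, "PFS and OS will be estimated using Kaplan-Meier methods separately for each cohort" (13.5).

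**The concern.** Cohort is a confounder if it is related both to the outcome and to the marker. The documents point to both.

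- **Outcome.** The null response rates are 10% (Cohort A) and 4% (Cohort B) in 13.3.2. Section 13.4 expects DLT rates to differ between cohorts. Section 2.1 describes a poor outlook in relapsed Ewing sarcoma, and section 2.4 cites a median PFS of 10 months in two studies of SDH-deficient GIST.
- **Marker.** Section 2.5 describes STAG2, TP53 and CDKN2A mutations in a subset of Ewing tumors but few secondary mutations in SDH-deficient GIST. It adds that ctDNA has not been described in the latter. Section 9.1.2.1 collects different tubes in the two cohorts.
- **Exposure.** The starting palbociclib dose differs by cohort (section 5.1.1).

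Objective 1.4.3 looks for markers that might predict clinical benefit. A pooled association that reflects only Ewing sarcoma versus GIST would send that work in the wrong direction.

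**Working it through.** **1. The plan's own figures.** Section 13.6 gives no sample size, alpha or power. The nearest stated figures are the response designs that fix the cohort sizes, and they reproduce.

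- Cohort A, n = 15, reject at 4 or more responses: P(X ≥ 4) = 0.0556 at p = 0.10 and 0.909 at p = 0.40. The plan states 0.056 and 91%.
- Cohort B, stop if 0 of 7, succeed at 2 or more of 12: the sum over x = 1 to 7 of P(X₁ = x) × P(X₂ ≥ 2 − x), with X₁ ~ Bin(7, p) and X₂ ~ Bin(5, p), is 0.0698 at p = 0.04 and 0.9006 at p = 0.32. The plan states 0.07 and 90%.

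The marker tests therefore have about 15 + 12 = 27 patients.

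**2. How pooling misleads.** Suppose ctDNA is positive in 80% of Cohort A and 20% of Cohort B, and has no effect within either.

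- Positive group: 0.8 × 15 = 12 Ewing and 0.2 × 12 = 2.4 GIST, so 12/14.4 = 83% Ewing.
- Negative group: 3 Ewing and 9.6 GIST, so 3/12.6 = 24% Ewing.

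Comparing these groups is largely a comparison of the two diseases.

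**3. Size for the log-rank test.** Simulation with 15 + 12 patients, exponential PFS, censoring at 24 months, two-sided 0.05, no within-cohort effect, and 10,000 trials per row. The Cohort B median of 10 months comes from section 2.4. The Cohort A median and both positivity rates are assumptions.

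| Ewing median PFS (assumed) | ctDNA positivity A vs B (assumed) | Pooled | Stratified by cohort |
|---|---|---|---|
| 5 months | 70% vs 30% | 12% | 6% |
| 5 months | 80% vs 20% | 18% | 6% |
| 5 months | 80% vs 10% | 23% | 6% |
| 3 months | 70% vs 30% | 19% | 6% |
| 3 months | 80% vs 20% | 36% | 6% |
| 3 months | 80% vs 10% | 49% | 6% |
| 3 or 5 months | 50% vs 50% | 6% | 6% |
| 10 months (equal PFS) | 70% vs 30% to 80% vs 10% | 6% | 5% to 7% |

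Repeat runs move these values by about a percentage point, hence about 12% to 48% pooled against 5% to 8% stratified. Censoring at 18 months instead gives 10% to 48% pooled. The 6% in the last two rows is the small-sample level of the log-rank test, not confounding. In 18-month runs with medians of 5 or 3 versus 10 months and positivity of 70% vs 30% or 80% vs 20%, the median pooled event-rate ratio was 1.35 to 2.11, although the true within-cohort hazard ratio is 1.

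**4. Fisher's test.** Take a mutation in 50% of Cohort A and none of Cohort B (assumed), with response rates from 13.3.2. Apply Cohort B's stage 1 stop, which occurs with probability 0.96⁷ = 75% at a 4% response rate. Pooled false-positive rates (20,000 trials each):

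- 40% vs 4%: 10%
- 10% vs 4%: 1%
- 40% vs 32%: 4%
- 10% vs 32%: 2%

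For this marker, only one of the four pairings exceeds 5%.

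**The case against.** **Pooling is inferred, not stated.** The phrase about patients who begin treatment grammatically governs only the summary statistics. The test sentences name no population, and with the rest of section 13 organised by cohort, an analyst might do the same here. This stands as a limit on the claim: the documents do not say that the tests are pooled. But 13.6 gives no instruction to split or stratify, and the same sentence settles either reading.

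**The size rests on assumptions.** The documents give neither an Ewing median PFS nor ctDNA positivity for either cohort. This stands. The upper end needs both the shorter Ewing median and the widest positivity split.

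**A reader might infer that the mutation test is badly inflated as a rule.** Pairing Cohort A's alternative response rate with Cohort B's null, and always enrolling 12 GIST patients, gives 18%. That ignores the stage 1 stop, which brings it to 10%, and the other pairings give 1% to 4%. More extreme marker splits can do worse, but the documents do not establish such splits.

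**A reader might also infer immortal-time bias.** Objective 1.4.1 is "To evaluate serial measurements of circulating tumor DNA burden as a surrogate marker of response to protocol therapy", and sampling continues to progression. However, 13.6 never says that patients are classified by ever clearing ctDNA on treatment. It uses serial values for relative changes, rank tests and plots. What remains is that the sample defining positivity is not named, which is a missing detail rather than a biased analysis.

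**The analyses are exploratory.** No alpha or decision rule is attached, and 13.6 gives graphical display the main role in forming hypotheses. This stands and limits the severity.

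**Conclusion.** The concern holds at minor severity. As written, 13.6 leads most naturally to marker tests that mix Ewing sarcoma with SDH-deficient GIST, and the documents themselves give reasons to expect the diseases to differ in outcome and in markers. For the ctDNA log-rank test, false positives would be about 12% to 48% pooled against 5% to 8% stratified. That range is conditional on a GIST median of 10 months, an assumed Ewing median of 3 to 5 months, and assumed positivity from 70% vs 30% to 80% vs 10%. If either PFS or positivity is the same in the two cohorts, there is no inflation. The documents do not support a general inflation figure for the Fisher test or a finding of immortal-time bias. The primary, secondary and safety conclusions do not depend on 13.6.

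**What to change.** In section 13.6:

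- Present marker summaries, box plots and spaghetti plots by cohort.
- Test associations stratified by cohort: stratified log-rank with a cohort-stratified Cox hazard ratio for ctDNA, van Elteren in place of the pooled Wilcoxon, and an exact stratified test in place of the pooled Fisher.
- Label any pooled result descriptive.

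Optionally, name the Cycle 1 Day 1 sample as the one that defines ctDNA positivity for the log-rank test.

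This changes wording only. Cohort is already recorded, and no samples, visits or patients are added. The price is power. A marker found in only one disease is informed by that cohort alone, and with 1 responder among 12 patients the smallest possible Fisher p-value is 1/12 = 0.083. The text should say that these tests are expected to have little power, so that a null result is not read as evidence against a marker.

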### 2.2.1.2 Clinical experience with IGF pathway inhibitors in Ewing sarcoma

These preclinical results have translated into clinical activity for IGF-1R monoclonal antibodies in patients with relapsed or refractory Ewing sarcoma. A phase 2 study of ganitumab included 18 patients with Ewing sarcoma. One patient had a confirmed partial response (6% response rate). Closer evaluation of the data demonstrated that 6/18 (33%) patients had tumor regression of at least 10%. In Children's Oncology Group (COG) protocol ADVL0712, one of 10 patients with Ewing sarcoma treated with cixutumumab at the 6 mg/kg dose level had a confirmed partial response and 4 additional patients had stable disease for at least 3 cycles. At the 9 mg/kg dose level, 2 of 20 patients had RECIST partial responses. Of the 16 patients with Ewing sarcoma treated on a phase 1 study of figitumumab, one patient had a complete response, one patient had a partial response, and 6 patients had stable disease for more than 4 months (12.5% response rate). A phase 2 study of figitumumab in 106 patients with relapsed or refractory Ewing sarcoma demonstrated a 14% response rate. A phase 1 study of dalotuzumab included 6 patients with Ewing sarcoma, one of whom had a mixed response.

[REDACTED]

[REDACTED]

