## 2.4 Rationale for evaluation of palbociclib and ganitumab in SDH-Deficient GIST

GIST is among the most common soft tissue sarcomas, with an estimated annual incidence in the US of 6,000 cases. While activating mutations in the receptor tyrosine kinase *KIT* represent the most common oncogenic driver in this disease, 10-15% of cases are characterized by loss of the succinate dehydrogenase (SDH) complex, leading to altered metabolism and epigenetic dysregulation. Patients with metastatic or unresectable SDH-deficient GIST are treated with tyrosine kinase inhibitors as standard therapy, though response rates are modest and more targeted therapies are urgently needed.

Prospective trials studying effects of treatment in SDH-deficient GIST are limited. As compared to imatinib, sunitinib demonstrated activity in a cohort of 7 patients, with one patient achieving a partial response. In a study of regorafenib which included 6 SDH-deficient GIST patients, two of these patients experienced a PR, with a median PFS of 10 months. In a recent study of linsitinib in SDH-deficient GIST, no responses were seen, and median PFS was 10 months.

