### 11.2.3 Response Criteria

#### 11.2.3.1 Evaluation of Target Lesions

**Target lesions:** All measurable lesions up to a maximum of 2 lesions per organ and 5 lesions in total, representative of all involved organs, should be identified as **target lesions** and recorded and measured at baseline. Target lesions should

be selected on the basis of their size (lesions with the longest diameter), be representative of all involved organs, but in addition should be those that lend themselves to reproducible repeated measurements. It may be the case that, on occasion, the largest lesion does not lend itself to reproducible measurement in which circumstance the next largest lesion which can be measured reproducibly should be selected. A sum of the diameters (longest for non-nodal lesions, short axis for nodal lesions) for all target lesions will be calculated and reported as the baseline sum diameters. If lymph nodes are to be included in the sum, then only the short axis is added into the sum. The baseline sum diameters will be used as reference to further characterize any objective tumor regression in the measurable dimension of the disease.

Complete Response (CR): Disappearance of all target lesions. Any pathological lymph nodes (whether target or non-target) must have reduction in short axis to <10 mm.

Partial Response (PR): At least a 30% decrease in the sum of the diameters of target lesions, taking as reference the baseline sum diameters.

Progressive Disease (PD): At least a 20% increase in the sum of the diameters of target lesions, taking as reference the smallest sum on study (this includes the baseline sum if that is the smallest on study). In addition to the relative increase of 20%, the sum must also demonstrate an absolute increase of at least 5 mm. (Note: the appearance of one or more new lesions is also considered progressions).

Stable Disease (SD): Neither sufficient shrinkage to qualify for PR nor sufficient increase to qualify for PD, taking as reference the smallest sum diameters while on study.

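### Section 13.6 links markers to tumour response only through the PR-or-better cut; a rank analysis of percent change in target-lesion size should be added alongside

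*Combined protocol and SAP*

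**What the plan says.** Section 13.6 sets two response-based marker tests. For continuous marker modulation, the association with "b) clinical response of partial response or better will be tested using a Wilcoxon rank-sum test". For mutations: "Secondary somatic mutations will be analyzed from tumor material and tested for association with objective response", by Fisher's exact test. All of these studies "are considered exploratory". No significance level, sidedness, minimum responder count or fallback is given. The section's population is described as "Within the group of patients who begin treatment with palbociclib and ganitumab", without saying whether the tests are run per cohort or pooled.

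Section 11.2.3.1 makes the finer measurement available: "The baseline sum diameters will be used as reference to further characterize any objective tumor regression in the measurable dimension of the disease". PR is a 30% fall on that scale. The Study Calendar (section 10, note 9) schedules restaging in cycles 2, 4, 6, 8, 10 and 12.

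Section 13.3.2 sets 15 evaluable patients for Cohort A (10% null, 40% alternative) and 7 + 5 = 12 for Cohort B (4% null, 32% alternative), with Cohort B stopping at 0 responders of 7.

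**The concern.** Splitting patients at a 30% reduction treats a 25% shrinkage and frank progression as the same outcome. With 12 to 15 patients and low response rates, the responder group may be empty or hold one patient, and the response-based test is then impossible or cannot be informative.

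The plan's background shows that there can be information below the cut. In the earlier ganitumab study, one of 18 Ewing patients had a confirmed PR (6%), yet section 2.2.1.2 adds: "Closer evaluation of the data demonstrated that 6/18 (33%) patients had tumor regression of at least 10" per cent.

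At stake are the response-based parts of objectives 1.4.1 (ctDNA as a marker of response) and 1.4.3 (predictive markers of clinical benefit). Mutations are the most exposed, because section 13.6 gives them no outcome test other than Fisher against objective response.

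**Working it through.** **Inputs.** Sample sizes, response rates and the Cohort B stop come from section 13.3.2. Two-sided 5%, the marker-tumour correlation and complete samples are assumptions; the plan gives none of them.

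**The plan's own figures reproduce.** Cohort A, at least 4 of 15: 0.0556 at 10% and 0.909 at 40% (stated 0.056 and 91%). Cohort B, at least 1 of 7 and then at least 2 of 12: 0.0698 at 4% and 0.9006 at 32% (stated 0.07 and 90%).

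**Smallest attainable p-values, per cohort.** With r responders among n patients, the minimum two-sided exact Wilcoxon p is 2/C(n,r).
- r = 0: no test.
- r = 1: 2/15 = 0.133 and 2/12 = 0.167. The Fisher minimum, when the one responder is the one mutated patient, is 1/15 = 0.067 and 1/12 = 0.083.
- r = 2: 2/105 = 0.019 and 2/66 = 0.030, so p<0.05 needs complete or nearly complete separation.

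**Chance of 0 or 1 responders.**
- Cohort A at 10%: 0.9^15 + 15 × 0.1 × 0.9^14 = 0.206 + 0.343 = 0.549. At 40%: 0.005.
- Cohort B at 4%, all 12 enrolled: 0.96^12 + 12 × 0.04 × 0.96^11 = 0.613 + 0.306 = 0.919. With the two-stage rule: 1 − 0.070 = 0.930, including 0.96^7 = 0.751 for stopping at 7 with none. At 32%: 0.065 with all 12 enrolled, 0.099 with the two-stage rule.

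**Power for a continuous marker.** Marker and tumour change were simulated as bivariate normal with correlation ρ; responders are those below the quantile that gives the design response rate. The planned exact Wilcoxon on responder status is compared with Spearman on the continuous change.

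| Design alternative | ρ | PR cut | Rank analysis |
|---|---|---|---|
| A, 40% | 0.5 | 27% | 43% |
| A, 40% | 0.6 | 41% | 63% |
| A, 40% | 0.7 | 57% | 81% |
| B, 32% | 0.5 | 19% | 33% |
| B, 32% | 0.6 | 28% | 50% |
| B, 32% | 0.7 | 40% | 68% |

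Runs differ by a point or two with simulation error and with how the Spearman critical value is obtained. At ρ = 0.5 the share lost is 1 − 27/43 = 37% in A and 1 − 19/33 = 42% in B. Another run gave 28% against 42% and 20% against 32%, a loss of 33% and 38%. Roughly 35 to 40% is a fair summary.

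At the null rates with ρ = 0.5, Cohort A gives about 10% against 43%. Cohort B gives about 1% against 21% once the stop at 0 of 7 is applied; the 34% seen without the stop assumes that all 12 patients enrol.

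**A different marker model.** If the marker shifts by an assumed 1.5 SD in responders and has no gradient otherwise, the ranking reverses: about 65% (PR cut) against 48% (Spearman) in A at 40%, and 46% against 29% in B at 32%.

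**Pooled, n = 27, 1 responder.** Wilcoxon minimum 2/27 = 0.074; Fisher minimum 1/27 = 0.037.

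**The case against.** The strongest reply is that section 13.6 declares these studies exploratory, sets no alpha, presents the comparisons with box plots and relies on graphics to develop hypotheses. Significance is then the reviewer's yardstick. That stands as a limit on severity. It does not remove the point, because the section does plan formal tests.

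Several stronger readings are tempting, and the documents do not support them.
- A reader might infer that the planned tests lose most of their power. That is true with 2 responders (at ρ = 0.6, 20% against 63% with n = 15), but not at the design alternatives. Large losses arise where responders are few, which is also where the trial would conclude against further study.
- A reader might infer that the correlative objectives go unanswered. Objective 1.4.2 is served by the change-from-baseline summaries and spaghetti plots, objective 1.4.4 is banking, and ctDNA positivity also has log-rank tests against PFS and OS. The DLT comparison does not use response either.
- A reader might infer that 1 responder rules out p<0.05 in any analysis. Pooled, Fisher can reach 0.037, and the plan does not say which applies.
- A reader might infer that percent change is always the better outcome and should replace the PR cut. The gain follows from assuming a graded relation, and it reverses if the marker tracks responder status alone.
- The linsitinib result in section 2.4 ("no responses were seen, and median PFS was 10 months") supports a time-to-event outcome. It says nothing about shrinkage below the cut.

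There are also practical objections to percent change, and they stand. Section 5.3.3 allows surgery or radiotherapy after confirmed response, which could contaminate an uncapped best change. A patient with slight target shrinkage and a new lesion is PD under the overall response table in section 11.2.3.5, but would look like a shrinker. Central review (section 11.3) covers confirmed responders only. The fix answers the first two; the third remains as a limitation.

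**Conclusion.** The point holds as a cheap improvement to an exploratory analysis. Section 13.6 uses only the PR cut to relate marker modulation and mutations to tumour response, although a finer scale is already recorded. Under per-cohort testing, the chance that the tests are impossible or cannot reach two-sided 0.05 is 55% in Cohort A at 10% response and 92 to 93% in Cohort B at 4%. Those figures are exact. The loss of roughly 35 to 40% of power at the design alternatives rests on an assumed graded correlation of 0.5 and a two-sided 5% level. It applies to the continuous-marker test; for Fisher, only the minimum p-values are claimed. Because a responder-only marker would favour the planned test, the two analyses belong side by side. No primary or secondary conclusion is affected.

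**What to change.** In section 13.6, keep the planned tests and add:
- a Spearman correlation of marker change with best percent change from baseline in the sum of target-lesion diameters;
- a Wilcoxon rank-sum test of that percent change by mutation status.

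State the rules with them:
- use only assessments up to the earliest of first progression, local surgery or radiotherapy, or non-protocol anti-cancer therapy;
- give the worst rank to any patient whose best overall response is PD, including progression by new lesion, by non-target disease or on clinical grounds;
- say whether each test is run per cohort or pooled;
- report the PR-based results descriptively when there are fewer than 2 responders.

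The cost is a few sentences of SAP text and a few lines of code, with no new data. The downsides are a few more exploratory tests and, for patients without a confirmed response, reliance on local measurements that are not centrally reviewed.
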